43. Other Waiver Types (Checklist).....	29
44. Vulnerable Populations (Checklist)	29

45.	Medical Devices (Checklist).....	35
46.	Export Control (Checklist)	36
47.	Data Transfer/Sharing (Checklist).....	36
48.	Specimen Transfer/Sharing (Checklist).....	37

1. Objectives

- 1.1. To measure the duration of viral shedding in respiratory secretions of patients with moderate or severe COVID-19 infection treated with the combination of Hydroxychloroquine and azithromycin.
- 1.2. Evaluate the case fatality rate, the clinical response and length of stay in hospitalized patients with moderate and severe COVID-19 infection.
- 1.3. To report the safety of the drug combination in hospitalized patients with moderate and severe COVID-19 infection.

2. Background

- 2.1. There is in vitro evidence of activity of Chloroquine against SARS-CoV 2. There are several studies that have shown that the use of Azithromycin may improve outcomes in viral respiratory tract infection. There is preliminary clinical data that suggest that the combination of HCQ and Azithromycin can decrease viral shedding in respiratory secretions and improve clinical outcome of patients with COVID-19 respiratory infection. Both drugs are relatively safe, and have been used for many years for other indications.

3. Study Design

- 3.1. Open label non-comparative prospective trial.

4. Inclusion and Exclusion Criteria

- 4.1. Adults aged ≥ 18 years of age to 74 years of age with lower respiratory infection with SARS-CoV2 documented by a positive RT-PCR in nasopharyngeal sample admitted to the University of New Mexico Hospital, with an oxygen saturation of less than 96%, on room air, or a respiratory rate >20 per minute, or HR >120 per minute of a $\text{PaO}_2/\text{FIO}_2 < 150$.
- 4.2. Patient with life expectancy >48 hours.
- 4.3. Pregnant women may be included if deemed necessary. There is insufficient information regarding the safety of hydroxychloroquine and azithromycin during pregnancy. Consequently, these medications are not recommended when pregnant or planning to become pregnant. However, investigators may prescribe hydroxychloroquine and azithromycin if deemed necessary.

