- The anticipated completion of the study is 5 years from date of IRB approval/study initiation.

7. Study Endpoints

- 7.1 Negative PCR test from nasopharyngeal swabs or oropharyngeal swabs in non-ventilator dependent patient or tracheal secretions in ventilator dependent patient on days 3, 6, and 14.
- 7.2 Resolution of clinical signs and symptoms of COVID19 infection, LOS, and patient outcome.
- 7.3 Drug related adverse event that motivates therapy discontinuation.

8. Research Setting

- 8.1. The study will be conducted at the University of New Mexico Hospital and Health Sciences Center.
- 8.2. Laboratory analysis will be performed at the UNM HSC, Tricore Reference Laboratories and/or the NM Department of Health.

9. Resources Available

- 9.1. [name] is the principal investigator for this research study. [name] is an Associate Professor with the Department of Family and Community Medicine. She also serves as the UNM School of Medicine Chancellor's Office as the Executive Director of Health Policy.
- 9.2. [name] is an Associate Professor within the Division of Infectious Diseases, Department of Internal Medicine.
- 9.3. [name], FACP is the Division Chief of Infectious Diseases, Department of Internal Medicine.
- 9.4. [name], FACS is a Senior Associate Dean for Clinical Affairs, UNM School of Medicine, the Chief Medical Officer, UNM Hospitals and a Clinician Ed - Professor: SOM Surgery General.
- 9.5. Patients will be recruited from those admitted to UNM Hospital and diagnosed with COVID-19, and will be dependent upon the number of patients actually admitted and progression of their disease as determined by the treating physician.
- 9.6. Depending on the patient's condition, care will be provided by the Hospital Medicine Teams or Intensive Care unit teams in general wards and ICU specially selected for COVID-19 patients.
- 9.7. Investigators will utilize the medications under an IND. At this time, it is unclear what company will supply the medications. Most probably, the supplier will have obtained and IND from the FDA. A modification will be submitted to clarify who will supply the study drugs.

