Nasopharyngeal and oropharyngeal swabs will be collected from the participants on day 3, 6 and 14. In intubated patients in which an oropharyngeal sample cannot be obtained, alternatively a tracheal secretion sample can be obtained.
- 12.5. Information from clinical parameters will be obtained from the electronic medical record. A separate electronic dataset (using RedCap) will be constructed to capture the most important clinical information on the patients at the time of presentation including the following: demographic information (gender, age,

DOB, place of residence, ethnicity and race), presenting and daily symptoms and signs (including fever, cough, SOB, sputum production, anosmia, hyposmia, fatigue, sore throat, nasal congestion, diarrhea, headache, vital signs, pulmonary auscultatory findings), initial and subsequent results of laboratory tests (Arterial blood gases WBC, lymphocyte count, Hbg, platelet count, , PaO₂, O₂ saturation, AST, ALT, LDH, Alkaline phosphatase, creatinine, urea nitrogen, lactate level, , Fibrinogen or IL-6 levels if available) results of radiographic studies and microbiological results, need for oxygen or mechanical ventilation.

- 12.6. Each person participating in this Study will be assigned a randomly generated study ID that will be linked to identifiers (MRN, DOB) in a linking table to be kept separate from the research data. Data and specimens will be labelled with the study ID only. Only HRRC-approved members of the study team who have the appropriate training will have access to the data and identifiers. All data that we collect in this study will be entered into REDCap, a secure data-base, on a password-protected computer using a secure network. Any hard copy records/data will be kept in a locked file cabinet in the locked office of a designated member of the Study team. The specimens will be kept and stored in the Clinical and Translational Science Center at the UNM HSC and can only be accessed by the members of the study team. Investigators will transport the specimens to TriCore Reference Laboratories for lab analysis through standard transport hospital procedures. After testing, any left-over samples will be delivered in part to CDC for validation testing, and in part to the CTSC for genomic sequencing. Once data collection is complete, data will be de-identified by destruction of the linking table.

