- 15.5. The specimens will be kept and stored in the Clinical and Translational Science Center at the UNM HSC and can only be accessed by the members of the study team. Then specimens will be transported to TriCore Laboratory and can only be accessed by laboratory personnel for the purpose specified in the protocol.
- 15.6. Once data collection is complete, data will be de-identified by destruction of the linking table. Study records will be kept for 6 years past study closure.

16. Data and Specimen Banking: Not applicable

17. Risks to Subjects

- 17.1. Risks of hydroxychloroquine include headache, dizziness, loss of appetite, nausea, diarrhea, stomach pain, vomiting and skin rash.
- 17.2. Risks of azithromycin include mainly gastro-intestinal symptoms, as well as cardiovascular, genitourinary, nervous system, allergic reaction and fatigue.
- 17.3. Risk of retinopathy.
- 17.4. Administration of study drugs individually or in combination may have risks to the subjects that are currently unforeseeable. Review of the clinical record as well as monitoring by the DSMB as described above will be conducted to mitigate these risks.

- 17.5. Risks also include a loss of privacy and/or confidentiality. This will be mitigated by conducting all study activity in private areas of the hospital and labelling all data/specimens with a study ID.
- 17.6. Suicidal ideation is also potential risk.
- 17.7. Unforeseen risk to participants, and if applicable, to an unborn fetus.
- 17.8. Refer to the Protocol Appendix for the detailed list of risks associated with hydroxychloroquine and azithromycin.

18. Potential Benefits to Subjects

- 18.1. Participants may benefit from reduction in/elimination of the viral load associated with their condition, and a reduction of morbidity and mortality associated with COVID-19 infection and sequelae.

19. Recruitment Methods

- 19.1. Once the result of the initial COVID19 test is reported as positive, the provider will ask potential participants and/or their LAR for permission to be approached by a member of the research team for recruitment.

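### Objective 1.1 is a duration of shedding, but only PCR negativity on days 3, 6 and 14 is measured, so patients already negative at first dose count as cleared on treatment

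*Protocol*

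**What the plan says.** - **Objective (Protocol 1.1):** "To measure the duration of viral shedding in respiratory secretions" in patients given the combination. This is a time quantity.
- **Design (3.1):** "Open label non-comparative prospective trial".
- **Eligibility (4.1):** lower respiratory infection "documented by a positive RT-PCR in nasopharyngeal sample admitted to the University of New Mexico Hospital". No limit is set on how long before enrolment or first dose that sample may have been taken.
- **Recruitment (19.1):** the approach to the patient comes "Once the result of the initial COVID19 test is reported as positive". The section on waiver of consent adds a daily list of inpatients with a positive test. Neither passage sets a time limit.
- **Endpoint (7.1):** a negative PCR from nasopharyngeal or oropharyngeal swabs, or from "tracheal secretions in ventilator dependent patient on days 3, 6, and 14". Sections 12.4 and 12.11 use the same three days. None of them includes a PCR at first dose.
- **Data capture (12.5):** the REDCap dataset is to "capture the most important clinical information on the patients at the time of presentation". The list that follows covers presenting and daily symptoms, laboratory results and microbiological results. It names no date of symptom onset and no date of the qualifying PCR.
- **Day count:** no passage says from which day the swab days run. Only the dosing text in 12.3, which has a day 1, implies an origin.
- **Stopping rule (13.5):** one trigger is that fewer than 15% of patients reach an undetectable viral load on day 6. The first analysis comes after 20 patients (13.6).

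**The concern.** A duration needs a start and an end. Here the end is seen only at three visits, and no start is named. Status at the beginning of treatment is not observed either, so clearance before the first dose cannot be told apart from clearance after it.

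A control arm would carry the same admixture of already-negative patients and would largely cancel it in the comparison. This trial has none, so the admixture goes straight into the reported proportion. It raises the apparent clearance and shortens the apparent time to clearance from first dose. It also enters a stopping rule, where it works against the rule's purpose: patients who were negative before treatment help the trial past the 15% limit.

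**Working it through.** **Two patients side by side.** Patient A had a positive test some time ago, is negative at first dose and stays negative. Patient B is positive at first dose and clears by day 3. Under 7.1, 12.4 and 12.11 both are recorded as negative on days 3, 6 and 14. Both meet 7.1 at day 3 and both count in the day-6 proportion of 13.5. No planned measurement separates them.

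**What the visits can show.** The end of shedding lies before the day-3 swab, between days 3 and 6 (3 days wide), between days 6 and 14 (8 days wide), or after day 14. Without status at first dose, the first interval has no lower bound at the start of treatment. If first dose is day 1, the swabs fall 2, 5 and 13 days after it.

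**Effect on the day-6 rule at the first look.** The protocol gives no power or error figure to reproduce (5.3 declines a power analysis), so this is a new calculation.

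Inputs from the protocol: n = 20 and a limit of 15%. Since 0.15 × 20 = 3, the rule fires at 2 or fewer negatives and does not fire at 3 or more.

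Assumed inputs, not in the protocol:
- c = 10%, the clearance by day 6 among patients positive at first dose, chosen to lie below the limit;
- f, the share already negative at first dose, all of whom stay negative to day 6.

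Formulas: observed proportion p = f + (1 − f) × c, and P(fires) = (1 − p)^20 + 20p(1 − p)^19 + 190p²(1 − p)^18.

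| f | p | P(fires), n = 20 |
|---|---|---|
| 0% | 0.10 | 0.677 |
| 10% | 0.10 + 0.90 × 0.10 = 0.19 → 0.19 | 0.239 |
| 20% | 0.20 + 0.80 × 0.10 = 0.28 | 0.053 |

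**Extreme case, c = 0 (nobody clears after first dose).** Then p = f. The chance of 3 or more negatives, so that this rule does not fire, is 7.5%, 32.3%, 59.5%, 79.4% and 96.5% for f = 5%, 10%, 15%, 20% and 30%.

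These figures show how sensitive the rule is. They do not estimate f.

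**The case against.** **Most tests are probably recent.** Recruitment follows the initial positive result, a daily list of positives is generated, 4.1 requires signs of current illness, and 4.6 excludes two groups of transferred patients. This stands, and it makes a large already-negative share less likely. It does not set a window. Section 12.10 also brings in five patients treated before protocol approval.

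**A reader might infer that no start point is captured at all.** The documents do not support that. The list in 12.5 is open-ended, draws on the medical record and includes microbiological results, so the qualifying-PCR date is unnamed rather than unavailable. The onset date is likewise not named. Even with the PCR date in hand, status at first dose would remain unknown.

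**A reader might infer that durations will be overstated by up to 8 days, because a clearance between days 6 and 14 would be dated to day 14.** Nothing in the protocol says so. Treatment of interval-censored times can properly be left to a statistical analysis plan.

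**The rule in 13.5 speaks of patients achieving an undetectable load, which could imply prior detectability.** That is a fair reading, but the planned data give no way to apply it.

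**The three visits are a deliberate choice under supply and exposure limits (9.8, 12.7).** That stands. The sparse schedule is not itself an error, and no reference to three visits here should be read as a call for more. The protocol's fault is to call the result a duration and to leave the starting status open.

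**A later analysis plan could handle this.** Only in part. It can define evaluable sets and censoring, but it cannot restore an onset date that was never recorded. Under 12.6 and 15.6 the linking table is destroyed once data collection is complete, so the chart could not then be consulted.

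**Conclusion.** The point holds. The protocol sets a duration as its objective and plans to measure negativity at three visits. It has no limit on the age of the qualifying PCR, no PCR at first dose, no named onset or qualifying-PCR date, and only an implied origin for the swab days. Patients already negative at first dose therefore count as cleared, in 7.1 and in the day-6 rule, and the direction of the bias in clearance is upward.

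Its size cannot be derived from the documents. The fall from 68% to 24% to 5% rests on an assumed 10% true clearance, on assumed already-negative shares of 0%, 10% and 20%, and on those patients staying negative. It covers only the first look at 20 patients, although 13.4 proposes further analyses every 20, and it leaves aside the two other triggers in 13.5. A reader might infer that the stopping rule is known to fail; the protocol does not support that, because the share already negative may be small.

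Correcting this would not separate drug effect from spontaneous clearance. A single-arm design cannot do that, even with a perfect baseline.

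**What to change.** 1. State that swab days are counted from first dose, and whether that day is day 0 or day 1.
2. Add two named REDCap fields: date of symptom onset and collection date of the qualifying PCR.
3. Base the 7.1 analysis and the day-6 proportion in 13.5 on patients whose last positive PCR was collected within a prespecified window before first dose (for example 72 hours). Report the remaining patients separately.
4. Describe the result as clearance by visit, or as interval-censored time from first dose using actual swab dates. If time from symptom onset is also reported, use each patient's own intervals, because the fixed visit days do not apply on that scale.

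The cost is two dates taken from the record or the patient, one definition and one evaluability rule, with no extra swab. The evaluable set becomes smaller, so 20 evaluable patients take longer to reach, and the clearance figure may be less favourable. The window reduces the bias without removing it, since a patient can turn negative between the test and the first dose. A PCR at first dose would settle that directly, but it draws on the swab supply that 9.8 seeks to protect, so it is an option and not the minimum.

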- 12.7. EKG or direct QtC calculation based on telemetry strip will be obtained at baseline as well as daily to exclude individuals with prolonged QT while on both agents. Investigators are limiting exposure and PPE use for a technician doing these tests. As such, this should not need to be done daily. Investigators calculate the QtC on the telemetry and are working on getting an EKG machine to be put in the ICU so the nurse could do it as needed. Investigators are having a hard time getting echos or any other procedure done in the ICU unless the investigators do it as no one wants to come in and we are running through our PPE supply.
- 12.8. Continue to follow-up with participants at home via phone call if participants discharged <14 days.
- 12.9. Continue to follow-up with participants if they are in the hospital > 14 days.
- 12.10. There are 5 patients who received the combination product before the approval of the protocol. These patients will be contacted via phone, consented via phone, after which, their data will be extracted as outlined in the protocol.
- 12.11. Important variables are as follows:
 - Result of the RT PCR test done on days 3, 6 and 14 as well as the determination i.e. positive or negative.

- Overall clinical evaluation of the patients as determined by the treating provider.
- Frequency of Complications related to COVID19 (ARDS, AKI, Metabolic Acidosis, Shock, Secondary infections, Multi-organ failure and death)
- Final disposition of the patient.
- Frequency of adverse events (including GI symptoms, QTc prolongation, visual disturbances, retinopathy)

13. Provisions to Monitor the Data to Ensure the Safety of Subjects

13.1. A DSMB will be convened to include clinicians specializing in infectious diseases and biostatisticians. The roster will be provided in a Modification for HRRC approval once the DSMB has been created.

13.2. Review of data after 20 participants have been enrolled.

13.3. Considering the novelty and rapidly changing situation of the COVID-19 pandemic, the investigators will review relevant publications that may help informed decisions related to the efficacy and safety of the investigational products.

13.4. The procedures for analysis and interpretation of the safety data.

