The occurrence of any serious adverse event will be notified to the HRRC in accordance to GCP regulations. An analysis of all adverse events will be presented with the analysis of the first 20 patients enrolled and periodically thereafter. We propose to conduct periodic analysis every 20 patients.

13.5. The conditions that would trigger a suspension or termination of the research (i.e., stopping rules), are as follows:

If available published information convincingly reports non-efficacy or significant safety concerns about HCQ+Azithromycin combination

If in the opinion of the investigators an unexpectedly high incidence of serious adverse events is detected during the trial.

If during the preliminary analyses less than 15% of the patients achieve and undetectable viral load on day 6.

13.6. The plan for reporting findings to the sponsor, investigators, and HRRC. A preliminary analysis of the study end points will be performed after 20 patients have been enrolled and end-points reached. The results will be presented to the HRRC and investigators.

14. Withdrawal of Subjects

14.1. Subjects will be withdrawn if the PI determines, in consultation with the treating clinician(s) that continuation in the study is not in the participant's best interest. Subjects may also withdraw (or be withdrawn by their LAR at their

request at any time during their participation in the study by contacting a member of the study team.

- 14.2. If a patient develops a serious adverse event that may be probably or definitely related to either drug, that may trigger the discontinuation of the offending drug.
- 14.3. If a participant is withdrawn from the study, chart review will continue to be performed to track the participant's clinical outcomes.
- 14.4. Data and specimens collected before withdrawal will not be removed from the study.

15. Data Management/Confidentiality

- 15.1. Participants will be assigned a randomly generated study ID that will be linked to identifiers (MRN, DOB) in a linking table to be kept separate from the research data. Data and specimens will be labelled with the study ID only.
- 15.2. Only HRRC-approved members of the study team who have the appropriate training will have access to the data and identifiers.
- 15.3. Data will be entered into REDCap on a password-protected computer using a secure network.
- 15.4. Any hard copy records/data will be kept in a locked file cabinet in the locked office of a designated member of the study team

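### Section 12.11 assigns death, shock, AKI and multi-organ failure to COVID-19 by its heading, and no attribution method is given, so drug-caused events can be left out of the safety summary

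*Protocol*

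**What the plan says.** Objective 1.3 is to report the safety of the drug combination. Section 3.1 describes an open-label trial without a comparator.

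Section 12.11 names two separate harm variables. One is "Frequency of Complications related to COVID19 (ARDS, AKI, Metabolic Acidosis, Shock, Secondary infections, Multi-organ failure and death". The other is "Frequency of adverse events (including GI symptoms, QTc prolongation, visual disturbances, retinopathy". Final disposition is a further item in the same list.

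The only safety endpoint, section 7.3, is "Drug related adverse event that motivates therapy discontinuation".

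On reporting, section 13.4 states: "The occurrence of any serious adverse event will be notified to the HRRC in accordance to GCP regulations". It adds: "An analysis of all adverse events will be presented with the analysis of the first 20 patients enrolled and periodically thereafter". Section 13.5 allows suspension or termination if the investigators judge that serious adverse events are more frequent than expected.

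The protocol treats cardiac harm as foreseeable. Section 4.6 excludes prolonged QTc (unless the treating physician judges that benefit outweighs risk) and users of several cardiac medicines. Section 12.7 says "EKG or direct QtC calculation based on telemetry strip will be obtained at baseline as well as daily". Section 17.2 says "Risks of azithromycin include mainly gastro-intestinal symptoms, as well as cardiovascular, genitourinary, nervous system, allergic reaction and fatigue".

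**The concern.** Section 12.11 divides harms by presumed cause. The gravest outcomes appear by name only in the list headed as COVID-19 complications. The adverse-event list names the electrocardiographic warning sign, QTc prolongation, but not the clinical events it warns of. Ventricular arrhythmia, syncope and cardiac arrest are named in none of sections 7, 12.5 and 12.11.

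A randomised trial could tolerate loose attribution, because an excess of deaths or organ failure in one arm would show whatever the label. Here there is no second arm. What the trial can say for Objective 1.3 depends on which events enter the safety summary. If cause is settled by the heading under which an event is filed, the summary can understate harm and nothing else in the design would reveal it.

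**Working it through.** The protocol gives no figure to reproduce on this point, so the check is a comparison of its provisions.

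**1. Where each event has a named place**

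| Event | 12.11, COVID-19 complications | 12.11, adverse events | Recorded elsewhere without a cause |
|---|---|---|---|
| Death | named | not named | case fatality (1.2), patient outcome (7.2), final disposition (12.11) |
| Shock | named | not named | vital signs (12.5) |
| AKI | named | not named | serial creatinine and urea nitrogen (12.5) |
| Multi-organ failure | named | not named | component laboratory results (12.5) |
| QTc prolongation | not named | named | QTc measurement (12.7) |
| Ventricular arrhythmia, arrest, syncope | not named | not named | no named field |

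The adverse-event list is introduced as non-exhaustive, so "not named" does not mean excluded.

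**2. Two on-treatment deaths from arrhythmia**

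- *Recognised as an adverse event.* The open list in 12.11 admits it. Section 13.4 requires notification and inclusion in the periodic analysis, and it counts towards 13.5.
- *Not recognised as an adverse event, for example a sudden death in a patient already severely ill.* It is filed under COVID-19 complications, case fatality and final disposition. Section 7.3 may not count it, since no decision to stop therapy need have been taken. Sections 13.4 and 13.5 act on events classed as adverse events, and nothing says that entries in the COVID-19 list are also so classed.

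The outcome turns wholly on recognition and attribution.

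**3. Is there an attribution method?** Section 14.2 grades relatedness, but only as a possible trigger for stopping a drug. Sections 11 and 13.1 to 13.6 name no assessor, scale or adjudication for deaths or organ failure.

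**4. How many events are exposed?** The protocol gives no event rate. As an assumption, let r be the true on-treatment rate of serious arrhythmia or arrest, with r = 1–2%. Expected events = N × r:

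- N = 200: 200 × 0.01 = 2 to 200 × 0.02 = 4.
- N = 1,000: 1,000 × 0.01 = 10 to 1,000 × 0.02 = 20.
- One review block of 20 patients (13.4): 20 × 0.01 = 0.2 to 20 × 0.02 = 0.4.

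These are events without a named field, not events lost. The number lost is N × r × (the fraction not recognised as adverse events). That fraction is unknown and can be zero, so N × r is only an upper bound. With fewer than one such event expected per block, classifying a single event differently can decide whether a block shows any.

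**The case against.** The strongest reply is that other provisions already cover this. The adverse-event list is open. Section 13.4 covers any serious adverse event without limiting it by cause, and requires analysis of all adverse events. Section 11 adds safety and unanticipated-problem reporting to the FDA, section 13.1 a DSMB, and section 17.4 review of the clinical record for unforeseen drug risks. Section 14.2 shows that attribution to a drug is contemplated. Death is also captured without a cause in three places. The two lists in 12.11 are not declared mutually exclusive, and gastrointestinal symptoms already overlap: diarrhoea is a daily symptom in 12.5 and falls within the adverse events in 12.11. Which terms to name in an open list is case-report-form detail.

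Much of this stands. A reader might infer that a fatal drug-induced arrhythmia will necessarily be reported as disease, or that such a death appears only as a COVID-19 death. The documents support neither inference, for the reasons just given. The kidney example is also weaker than the cardiac one: section 17.2 mentions genitourinary risk rather than kidney injury, and serial creatinine allows later reassessment. The absence of arrhythmia from an open list would not by itself be a finding.

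What the reply does not remove is the dependence on classification. The 13.4 safeguards operate once someone calls an event adverse, while 12.11 offers a different place for the most serious ones. The milder reading, that the COVID-19 row holds only events judged to be due to disease, leaves the same gap: someone must make that judgement and no method is stated. An analysis plan could choose denominators and tables, but could not recover a preceding arrhythmia that was never recorded.

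**Conclusion.** The concern holds as a risk of misattribution. Section 12.11 labels death, shock, AKI and multi-organ failure as COVID-19 complications. Section 7.3 counts only drug-related events that prompt discontinuation, and no method of attributing deaths or organ failure is given. In a trial without a comparator, drug-caused events can therefore be tabulated as disease and left out of the safety summary and of the incidence judged under 13.5. Events recognised as adverse should still be caught by 13.4 and the open list.

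The loss cannot be sized from the protocol. The 2–4 events per 200 and 10–20 per 1,000 rest on an assumed 1–2% rate and are upper bounds. The conclusion itself does not need them: it rests on the wording of 7.3, 12.11 and 13.4 and on the design in 3.1. The viral-shedding endpoint and the count of deaths are unaffected. What is weakened is the answer to Objective 1.3, and the point should be corrected.

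**What to change.** - In 12.11, replace the COVID-19 complications item by complications of any cause after first dose. Record relatedness to each drug and to the disease in a separate field, and state who assesses it and on what scale.
- Include all-cause death, shock, AKI and multi-organ failure in the safety summary as well as the disease summary, and state that they count towards the serious-adverse-event incidence in 13.5.
- Record ventricular arrhythmia, cardiac arrest and syncope from the medical record. For each death, record any preceding arrhythmia and the last available QTc with its date.

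No new test is needed. The cost is a few REDCap fields completed from the chart already used under 12.5. The last QTc may be old or missing, since 12.7 describes limits on obtaining it, so its date matters. The drawback is that the safety table will contain disease-caused events and look less favourable. Showing the relatedness assessment beside the all-cause counts lets readers judge this for themselves.

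Separately, 12.7 states both that QTc is obtained daily and that this should not have to be daily. Those statements must be reconciled by the investigators.

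### Does the 15% day-6 stopping rule need a stated denominator, a minimum count and a named look before it can be used?

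*Protocol*

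**What the plan says.** Section 13.5 of the protocol gives three conditions for suspending or ending the research. Two are matters of judgement: convincing published evidence, and an unexpectedly high rate of serious adverse events. The third is numeric: "If during the preliminary analyses less than 15% of the patients achieve and undetectable viral load on day 6".

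Three nearby clauses describe looks at the data:

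- Section 13.2: "Review of data after 20 participants have been enrolled".
- Section 13.4, on safety data: "An analysis of all adverse events will be presented with the analysis of the first 20 patients enrolled and periodically thereafter", followed by "We propose to conduct periodic analysis every 20 patients".
- Section 13.6: "A preliminary analysis of the study end points will be performed after 20 patients have been enrolled and end-points reached", with results going to the HRRC and the investigators.

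On sampling, section 12.4 states "Nasopharyngeal and oropharyngeal swabs will be collected from the participants on day 3, 6 and 14". Section 12.8 says "Continue to follow-up with participants at home via phone call if participants discharged <14 days", and section 4.2 requires only "Patient with life expectancy >48 hours". Section 12.10 brings in five patients treated before approval. Section 13.1 provides for a DSMB that includes biostatisticians.

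**The concern.** A numeric trigger needs a numerator, a denominator and a time, and section 13.5 states only the first plainly. Day-6 results could well be missing: patients who go home early are followed by telephone, no outpatient swab is described, and death before day 6 is possible. The rule does not say how such patients count, how many results must be in hand, or which of the looks it belongs to. The protocol also does not say whether the five patients of section 12.10 are among the first 20.

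This is the only numeric trigger for halting the trial, and the trial is open label. If the convention were chosen after the data were seen, the same results could halt the study under one reading and not under the other. A look with few day-6 results would also be more likely to cross by chance when true clearance is moderately above 15%.

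**Working it through.** **Which look.** Within section 13, a preliminary analysis is mentioned only in 13.5 and 13.6. Section 13.6 says what it covers (the study end points) and when it happens (20 patients, end points reached). Day-6 PCR negativity is a study end point under section 7.1, so the natural reading ties the rule to 13.6. Section 13.4 presents the adverse-event analysis alongside an analysis of the first 20 patients, so the two are distinct, and then proposes analysis every 20. That accounts for the plural in 13.5. Sections 13.2 and 13.4 count enrolment, but neither mentions the 15% rule.

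**Inputs.** From the protocol: a threshold below 15% and looks at multiples of 20. The protocol attaches no error rate or power to the rule, so there is no figure of its own to reproduce. True clearance rates and missing fractions below are assumptions.

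**Cut-off.** The rule is met at x clearances among n when x/n < 0.15.

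| n | 0.15 × n | Largest x that crosses |
|---|---|---|
| 20 | 3.00 | 2 |
| 14 | 2.10 | 2 |
| 13 | 1.95 | 1 |
| 40 | 6.00 | 5 |
| 34 | 5.10 | 5 |
| 33 | 4.95 | 4 |

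**Where the denominator matters.** Counting missing as not cleared fixes n at 20, with a cut of 2. Leaving them out gives the same cut of 2 for 14 to 20 results. The readings part only at 13 or fewer results, that is 7 or more of 20 missing: 2/20 = 10% crosses, 2/13 = 15.4% does not. At 40 patients they also part only at 7 or more missing: 5/40 = 12.5% crosses, 5/33 = 15.2% does not. With 12 results of 20 and true clearance 20%, crossing is P(X ≤ 2) = 55.8% with missing as failures and P(X ≤ 1) = 27.5% with missing left out. So the effect is large once it starts, but it needs 8 of 20 missing in that example.

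**First look with 20 results.** P(X ≤ 2 | 20, p) is 67.7% at p = 10%, 20.6% at 20%, 9.1% at 25% and 3.5% at 30%.

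**Fewer results.** At a true 25%, P(X ≤ 2 | n, 0.25) is 13.5% for n = 18, 19.7% for n = 16 and 28.1% for n = 14. The cut is 2 under both readings throughout, so naming a denominator would not alter these figures. They need a look taken with fewer than 20 day-6 results, and 13.6 does not call for a look at a bare enrolment count.

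**Repeated looks.** Exact recursion, true 25%, ten looks at every 20 enrolled up to 200:

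| Missing | Missing as failures | Missing left out |
|---|---|---|
| 10% | 19% | 18% |
| 20% | 32% | 23% |
| 30% | 52% | 32% |

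Looks at every 20 evaluable give 12%. In the bottom row, counting missing as failures makes the success rate 0.25 × 0.7 = 17.5%, close to the 15% line. Much of the 52% is therefore the definition at work, not chance.

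**The obvious rewording.** Suppose only patients with a day-6 PCR count, plus deaths before day 6 as failures. Assume 25% clearance overall and 30% discharged before day 6 who clear at rate q. Ignoring deaths, those tested then clear at r = (0.25 − 0.3q)/0.7, which is 18.6% at q = 40% and 14.3% at q = 50%. With 20 evaluable, the first look crosses 25% or 44% of the time, against 9.1% without selection. The look also comes later, at about 20/0.7 ≈ 29 enrolled. Where true clearance is only 10%, crossing falls from 84.2% (14 results at 20 enrolled) to 67.7% (20 evaluable).

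**The case for a change.** The strongest case for a change is that the trigger and its consequence are both written into the protocol, so its wording is not simply an analysis detail held elsewhere. The phrase about end points reached in 13.6 does not say which end points. A patient who went home or died before day 6 has reached an outcome without a day-6 swab, so 20 such patients need not mean 20 results. Repeats appear only in 13.4, under safety data, and the number of looks matters: at a true 20%, crossing is 20.6% with one look at 20 and 31.6% over five looks to 100. Clarifying wording would cost little.

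Part of this stands. The protocol does not say how an unswabbed patient counts, or whether the five earlier patients belong to the first 20, and the heading of 13.4 leaves some doubt about repeats. But if the end points of 13.6 include day 14 or length of stay, the look falls later, not earlier, so the open question is again only how unswabbed patients count. The literal wording of 13.5 already offers all patients as a default. Crossing leads to suspension or termination, not to an automatic end, and results go to the HRRC and investigators with a DSMB planned. A crossing produced by missing swabs would be plain to anyone who saw the count of results.

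**Conclusion.** No change to the plan is called for. The lack of a stated minimum and a named look is loose drafting that 13.4 and 13.6 together resolve well enough. The denominator is a real but narrow gap of the kind analysts fill sensibly, most simply by showing the result with missing swabs counted both ways. At the first look it alters the decision only if 7 or more of 20 day-6 results are absent, and then only for certain counts, such as 2 clearances.

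The protocol schedules a day-6 swab for everyone and gives no rate of early discharge, early death or missed swabs, so whether that point would be reached cannot be judged from it. The larger crossing probabilities rest on assumed missing fractions and on looks timed by enrolment. An evaluable-only rule swaps one bias for another and delays the look, so it is a trade-off and not a clear gain. This conclusion assumes that the rule is applied at the 13.6 analysis and that the number of day-6 results is reported with it.
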